#### **9.2.2.2. Major Secondary Endpoints**

Duration of response (DoR) will be duration from the date of the initial documentation of a response to the date of first documented evidence of PD (or relapse for subjects who experience CR). For those subjects who are still without progression/relapse, DoR will be censored at the last adequate tumor assessment.

PFS is defined as the duration from the date of the first daratumumab dose to the date of progression/relapse or death, whichever comes first. For those subjects who are still alive without progression/relapse, PFS will be censored at the last adequate tumor assessment.

Overall survival (OS) is defined as the duration from the date of the first daratumumab dose to the date of death. For those subjects who are still alive without progression/relapse, OS will be censored at the last date known to be alive.

Time to response is defined as the duration from the date of the first dose of daratumumab to the earliest date that a response (CR/PR) is first documented. For non-responders, it will be censored at the date of progressive disease/relapse or the date of the last adequate disease assessment, whichever comes first.

additional sampling is required. Procedures for sample collection, preparation, identification, storage, and shipment will be provided in the Laboratory Manual or equivalent document.

Additionally, blood samples should also be collected at the final visit from subjects who are discontinued from treatment. Subjects who discontinue treatment will also be asked to return for immunogenicity evaluation during the Follow-up Phase.

A blood sample should be drawn, if possible, for determination of antibodies to daratumumab any time an infusion reaction is observed or reported during the study. Daratumumab serum concentration will also be determined from the same infusion reaction sample for the purpose of interpreting immunogenicity data. These samples will be stored and evaluated if deemed necessary. If the infusion reaction results in treatment discontinuation, then subjects should undergo all scheduled safety and efficacy evaluations. Samples collected for the analysis of daratumumab immunogenicity/serum concentration may additionally be used to evaluate safety or efficacy aspects that address concerns arising during or after the study period or for the evaluation of relevant biomarkers by the sponsor or sponsor's designee.

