Alternatively, if the futility criteria are not met and if supported by the totality of the Stage 1 data, Stage 2 for that NHL subtype may be opened for accrual. If the required number of responses is observed prior to completion of enrollment in Stage 1, Stage 2 may be opened immediately upon completion of enrollment to Stage 1, if supported by the totality of data.

Stage 2, if opened, is designed to further evaluate safety and efficacy as well as to determine a threshold for CD38 expression that is associated with enhanced daratumumab activity. Supported by the preliminary activity observed in Stage 1, Stage 2 will enroll any subject in each NHL subtype. To mitigate the possibility that a low response may be observed due to low levels of

CD38 expression in enrolled subjects, the number of Stage 2 subjects with CD38 expression level <50% will be capped within each NHL subtype.

The target number of subjects in each stage by CD38 expression level is shown in table below.

Type of NHL	Number of Subjects			Overall Total
	Stage 1 CD38 expression level ^b ≥50%	Stage 2 (optional)		
		CD38 expression level ^a <50%	CD38 expression level ^b ≥50%	
MCL	20	≤30	≥50	100
DLBCL	15	≤20	≥20	55
FL	15	≤20	≥20	55

DLBCL=diffuse large B cell lymphoma ; FL=follicular lymphoma; MCL= mantle cell lymphoma

a. These subjects have tumors where <50% of the cells are positive for CD38 by immunohistochemistry.

[figure not shown]
b. These subjects have tumors where ≥50% of the cells are positive for CD38 by immunohistochemistry.

Subject participation will include a Screening Phase, a Treatment Phase, and a Follow-up Phase.

The Screening Phase will be up to 28 days prior to Cycle 1, Day 1. Prior to enrollment, subjects are required to provide tumor tissue to determine CD38 expression level by immunohistochemistry (IHC) at a central laboratory. An additional fresh biopsy should be obtained whenever possible even if an archival sample is provided.

The Treatment Phase will extend from Cycle 1, Day 1 until study drug discontinuation. After first dose, disease evaluations will occur every 8 weeks for the first 3 evaluations, then every 16 weeks for the next two evaluations and then every 24 weeks thereafter. Subjects will be treated until disease progression, unacceptable toxicity, or other reasons as listed in the protocol.

A schematic overview of the dosing schedule is presented as follows.

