2. GENERAL ANALYSIS DEFINITIONS

2.1. Visit Windows

Any analysis that uses time-to-event data will be based on the exact determination of time from first dose of daratumumab to the date of the event. For the calculation of time-to-event and duration-of-event variables, the difference between the start date and the end date plus 1 day will be used.

For analyses of data by cycle, if data are collected by date (ie, AE onset), the corresponding study evaluations will be assigned to actual sequential cycles, which are derived from the study treatment administration data. The start date of a particular cycle is defined as the date of the first dose of daratumumab of that cycle, and the end date of a cycle is the start date of the next cycle minus 1. For the last cycle, the end date is defined as the end of treatment visit date or the minimum of last study treatment date plus 30 days or subsequent anticancer therapy minus 1 day, if the end of treatment visit date is not available.

In general, if data (eg, laboratory and vital sign etc) are collected by cycle, the nominal cycle will be used to summarize data.

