4.3.1. Progression-free Survival (PFS)

Definition

PFS is defined as the duration from the date of the first daratumumab dose to the date of progression/relapse or death (prior to subsequent systemic anticancer therapy or withdrawal of consent to study participation or lost to follow-up) due to any cause, whichever comes first.

If a subject started subsequent therapy or withdrew consent to study participation or lost to follow-up, PFS will be censored at last disease assessment prior to the date of the start of subsequent therapy or date of withdrawal of consent or lost to follow-up. Subjects who have not progressed and are still alive at the cut-off date for analysis will be censored at the date of last disease assessment. Subjects without any post-baseline disease assessment will be censored at the date of first Dara dosing.

Analysis Methods

Analysis of PFS will be based on all treated population. The Kaplan-Meier method will be used to estimate the distribution of overall PFS for each NHL subtype. The median PFS will be provided. In addition, the number and percentage of subjects who had progression disease or were censored will be reported. The Kaplan-Meier PFS curve will also be plotted by NHL subtype.

Additionally, reasons for PFS and censoring will be summarized for all treated subjects.

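### SAP 4.3.1 gives two conflicting PFS rules for a subject who dies before any post-baseline disease assessment and does not say which one prevails

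*SAP*

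**What the plan says.** The event definition in SAP 4.3.1 reads: "PFS is defined as the duration from the date of the first daratumumab dose to the date of progression/relapse or death". Deaths count only if they occur "prior to subsequent systemic anticancer therapy or withdrawal of consent to study participation or lost to follow-up", and subject to that limit they count "due to any cause, whichever comes first".

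Three censoring sentences follow. The first covers subsequent therapy, withdrawal and loss to follow-up, and censors at the last disease assessment before that date. The second is expressly limited to living subjects: "Subjects who have not progressed and are still alive at the cut-off date for analysis will be censored" at the last disease assessment. The third is "Subjects without any post-baseline disease assessment will be censored at the date of first Dara dosing". It mentions neither vital status nor the absence of an event.

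Protocol 9.2.2.2 also counts death as an event and has a single censoring rule: "For those subjects who are still alive without progression/relapse, PFS will be censored at the last adequate tumor assessment". The protocol text available has no first-dose rule.

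On timing, SAP 1.1 says: "After first dose, disease evaluations will occur every 8 weeks for the first 3 evaluations". For durations, SAP 2.1 says that "the difference between the start date and the end date plus 1 day will be used".

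**The concern.** A subject who dies on day 30 without a scan is an event under the definition and is censored on day 1 under the third sentence. The second sentence and the protocol rule both carry an alive condition, so its absence from the third sentence could be read as deliberate. A programmer working line by line from the censoring rules could code the death as censored at first dose, where it adds nothing to the estimate.

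PFS is a major secondary endpoint assessed at the interim analysis, with Stage 1 cohorts of 20 (MCL), 15 (DLBCL) and 15 (FL), so a single subject carries visible weight. SAP section 1 adds that this document becomes the study SAP if the futility criteria are met, so the wording could govern final reporting.

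**Working it through.** The documents state no PFS median, event count or power, so there is no figure to reproduce. The check compares Kaplan-Meier PFS under the two readings.

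**Inputs from the documents.** The first scheduled evaluation is at week 8. With the plus-one-day convention that is 8 × 7 + 1 = day 57, and censoring at first dose is 0 + 1 = day 1. Stage 1 sizes are n = 20 and n = 15 (SAP 1.2).

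**Assumed inputs.** d deaths occur before the first scan, with no other early event or censoring. The documents give no value for d; the range used is about 5% to 20% of subjects.

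**Day 56, just before the first scan.**
- Deaths as events: S(56) = 1 - d/n.
- Deaths censored at day 1: no events have occurred, so S(56) = 1.000.
- Overstatement: d/n, which per death is 1/20 = 5 points or 1/15 = 6.7 points.

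**After the first scan.** With no later censoring, the censored reading lies above the event reading by the factor n/(n - d). For illustration, put the early deaths at day 29 and let the remaining subjects progress at weeks 8, 16 and 24 (days 57, 113 and 169) in roughly a 40/30/30 split. For n = 20 and d = 4, 16 subjects remain and 6, 5 and 5 progress at the three scans. Then S(57) = 10/20 = 0.500 with deaths as events and 10/16 = 0.625 with deaths censored; the ratio is 20/16 = 1.25.

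| n | d | S(56) event | S(56) censored | S(57) event | S(57) censored | Median event (day) | Median censored (day) |
|---|---|---|---|---|---|---|---|
| 20 | 1 | 0.950 | 1.000 | 0.550 | 0.579 | 113 | 113 |
| 20 | 2 | 0.900 | 1.000 | 0.550 | 0.611 | 113 | 113 |
| 20 | 4 | 0.800 | 1.000 | 0.500 | 0.625 | 57 | 113 |
| 15 | 1 | 0.933 | 1.000 | 0.533 | 0.571 | 113 | 113 |
| 15 | 2 | 0.867 | 1.000 | 0.533 | 0.615 | 113 | 113 |
| 15 | 3 | 0.800 | 1.000 | 0.467 | 0.583 | 57 | 113 |

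The median is the first time at which S is 0.5 or less. The curve is overstated in every row; the median moves only with the most early deaths.

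**Sensitivity of the median.** Now suppose that a fraction f dies before week 8 and the rest have exponential progression times, observed at the SAP 1.1 scans (weeks 8, 16, 24, 40 and so on).
- Assumed median 26 weeks: S(24) = 0.5^(24/26) = 52.7% with deaths censored. Multiplying by 1 - f gives 50.1%, 47.5% and 42.2% for f = 5%, 10% and 20%. The observed median stays at week 40 for f = 5% and changes between week 24 (events) and week 40 (censored) for f = 10% and 20%.
- Assumed median 13 weeks: S(8) = 65.3% with deaths censored, and 62.0%, 58.7% and 52.2% with deaths as events. S(16) is at most 42.6%, so the median is week 16 in every case. The week-24 gap is f × 0.5^(24/13) = f × 27.8%, or 1.4 to 5.6 points.

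The median therefore moves in two of these six scenarios. It does so because S(24) was assumed close to 50% and the next scan is 16 weeks later.

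**The case against.** The strongest reply is that there is no conflict. Censoring rules ordinarily apply only to subjects without an event, and the definition has already made an early death an event. The first two censoring sentences use a last disease assessment, a date that does not exist for an unscanned subject; the third merely supplies the missing date. This reading agrees with the protocol, and it is probably what was meant. But the SAP does not say so, and the condition written into the second sentence is missing from the third. The reporting text does not settle the matter: it counts subjects with progression or censoring and gives death no category of its own.

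A reader might infer more than the documents support:
- *That the SAP instructs the analyst to discard early deaths.* It does not. The text is an unresolved conflict, and one reading of it gives the correct result.
- *That such a subject disappears from PFS.* The subject stays in the all-treated set as a censored case. Reasons for PFS events and censoring are to be summarised, and the death also appears in OS and in the death tables and listing (SAP 5.2.1). The handling would be visible, although visibility does not correct the curve.
- *That the bias is worst in the aggressive subtypes.* No early-death rate is given for any subtype. At a fixed f, the week-24 gap above is smaller with the shorter median.
- *That median PFS would shift markedly.* This depends on the assumed inputs.

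The affected group may also be smaller than a count of deaths before week 8. Protocol 9.1.3 allows more frequent evaluation when clinically indicated, and 9.2.1.2 allows evaluation by physical examination, so some of these subjects may have had an assessment.

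**Conclusion.** The conflict is real and should be resolved before PFS is programmed. Applied literally, the third sentence can only raise PFS under the conditions used here: by d/n just before the first scan, and by the factor n/(n - d) afterwards if there is no later censoring. That is 5 to 20 points at day 56 for one to four deaths among 20 subjects, and 6.7 to 20 points for one to three among 15. These sizes rest on assumed values of d, and no statement about the median follows without further assumptions.

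The consequence is limited. PFS has no test or power statement in the SAP, the futility rule uses response counts, and ORR and OS do not depend on this sentence. Deaths after subsequent systemic therapy, withdrawal or loss to follow-up are not PFS events under the SAP in any case.

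**What to change.** Replace the last censoring sentence in SAP 4.3.1 with wording such as: *Subjects who are alive and have no post-baseline disease assessment will be censored at the date of first daratumumab dose; death before the first assessment (and before subsequent therapy, withdrawal or loss to follow-up) is a PFS event on the date of death.*

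Add that a subject censored for subsequent therapy, withdrawal or loss to follow-up, with no assessment before that date, is also censored at first dose whatever the later vital status. Without this clause, a subject who starts new therapy unscanned and later dies would be neither alive nor an event and would fall under no rule.

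As a minor alignment, use the protocol's last adequate assessment in the other censoring sentences and say what makes an assessment adequate. The SAP expects not-evaluable responses (4.2.2), and the protocol text available does not define the term.

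The cost is a few lines of SAP text, with no effect on data collection or sample size. Reported PFS may be slightly less favourable than under the literal reading.

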4.3.2. Overall Survival (OS)

Definition

Overall survival (OS) is defined as the duration from the date of the first daratumumab dose to the date of death. Subjects who withdraw consent from the study or are lost to follow-up will be censored at the time of withdrawal or lost to follow-up. Subjects who are still alive at the cut-off date for the analysis will be censored at the last known alive. The date of last known alive will be determined by the maximum collection/assessment date from among selected data domains within the clinical database.

Analysis Methods

Analysis of OS will be based on all treated population. The Kaplan-Meier method will be used to estimate the distribution of overall OS for each NHL subtype. The median OS will be provided. In addition, the number and percentage of subjects who had died or were censored will be reported.

4.3.3. Time to Response (TTR)

Time to response is defined as the duration from the date of the first dose of daratumumab to the earliest date that a response (CR/PR) is first documented. Time to response will be listed for responders.

4.3.4. Duration of Response

Duration of response (DoR) will be calculated and listed only for responders. It is defined as the duration from the date of the initial documentation of a response (PR or better) to the date of first documented evidence of PD (or relapse for subjects who experience CR) or death due to PD, whichever comes first.

A listing of subjects' first response, best response, TTR, DoR disease progressions and overall survival including NHL subtype, subject ID, baseline beta-microglobulin and CD38 expression level will be provided.

5. SAFETY

Safety assessment will be evaluated through AEs, clinical hematology and chemistry laboratory tests, ECGs, vital signs measurements, physical examination findings, and assessment of ECOG performance status score. All toxicities will be graded according to the NCI CTCAE Version 4.03. Safety analyses will be based on all treated population and presented by each NHL subtype.

5.1. Adverse Events

All adverse events whether serious or non-serious, will be reported from the time a signed and dated ICF is obtained until 30 days after the last dose of study treatment, until the subject withdraws consent for study participation, or until the subject starts subsequent anticancer therapy, whichever occurs first. AEs will be recorded in standard medical terminology and graded according to the National Cancer Institute Common Terminology Criteria for Adverse Events (NCI-CTCAE), Version 4.03. For AE reporting, the verbatim term used in the CRF by investigators to identify adverse events will be coded using the latest version of Medical Dictionary for Regulatory Activities (MedDRA) coding dictionary.

Unless otherwise specified, at each level (e.g., system organ class and/or preferred term) of subject summarization in reporting the incidence of the AE, a subject is counted once if one or more events were recorded.

All summaries of AEs will be based on treatment-emergent adverse events (TEAEs). TEAEs are defined as any AE that occurs after start of the first study treatment through 30 days after the last study treatment; or the day prior to start of subsequent anticancer therapy, whichever is earlier; or any AE that is considered drug-related (very likely, probably, or possibly related) regardless of the start date of the event.

The incidence of TEAEs will be summarized overall, by MedDRA system organ class (SOC) and preferred term, by toxicity grade, and by relationship to study treatment administration. Specifically, the following AE summaries will be presented by NHL subtype:

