2.8.1. Missing/Partial Adverse Event Onset Date

If the onset date of an adverse event is missing completely or partially, the following imputation rules will be used.

- When month and year are present and the day is missing,
 - If the onset month and year are the same as the month and year of first study treatment, the day of first study treatment or the day-component of the AE end date (possibly imputed) is imputed, whichever is earlier
 - If the onset month and year are not the same as the month and year of first study treatment, then the first day of the month is imputed
- When only a year is present or no components of the onset date are present,
 - If the onset year is the same as the year of first study treatment. If AE end date is available and is prior to first study treatment, the day and month of AE end date are imputed. Otherwise, the day and month of first study treatment are imputed
 - If the onset year is different from the year of first study treatment, the 1st of January is imputed
- If the onset date is completely missing, the date of first study treatment is imputed as the onset date.

No imputation will be done for partial or missing AE onset time.

If AE onset date needs imputation, but the AE onset time is available, the AE onset time will be dropped in the imputed AE onset date/time variable.

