5.1.3. Toxicity Grade 3 or 4 TEAEs

- Incidence of toxicity grade 3 or 4 TEAEs, by MedDRA SOC and preferred term

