5.1.6. Serious Adverse Events (SAEs)

- Incidence of treatment-emergent SAEs, by MedDRA SOC and preferred term
- Incidence of treatment-emergent SAEs considered by the investigator to be related to study treatment, by MedDRA SOC, and preferred term

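### The TEAE definition in SAP 5.1 has no worsening clause, so an unrelated AE that opens before first dose and becomes severe on daratumumab can drop out of several safety summaries if the worsening stays on its original record

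*SAP*

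**What the plan says.** SAP 5.1 gives two routes to treatment-emergent status. The first is a time window: "TEAEs are defined as any AE that occurs after start of the first study treatment through 30 days after the last study treatment", closing earlier if subsequent anticancer therapy starts. The second is causality: "any AE that is considered drug-related (very likely, probably, or possibly related) regardless of the start date of the event". The same section bases all AE summaries on TEAEs, and individual tables repeat the restriction, for example "Incidence of toxicity grade 3 or 4 TEAEs, by MedDRA SOC and preferred term" (5.1.3) and "Incidence of treatment-emergent SAEs, by MedDRA SOC and preferred term" (5.1.6).

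Collection starts before treatment. SAP 5.1 says AEs "will be reported from the time a signed and dated ICF is obtained until 30 days after the last dose of study treatment", subject to earlier stopping events, and SAP 1.1 says "The Screening Phase will be up to 28 days prior to Cycle 1, Day 1".

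SAP 2.8.1 and 2.8.2 give imputation rules for AE onset and end dates, including "If the onset date is completely missing, the date of first study treatment is imputed as the onset date". No rule in the supplied text defines a date of worsening or of grade change.

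**The concern.** An AE recorded during screening can be open at first dose and then worsen. The on-treatment part of that event is what a TEAE summary is meant to show. Under the SAP wording, an event with a pre-dose onset date counts only if the investigator considers it at least possibly related. For these events, inclusion in the TEAE tables therefore depends on the causality assessment.

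Three features of the plan raise the stakes. SAP 1.3 makes Grade 3 or 4 AEs and serious AEs part of the interim safety evaluation. SAP 1 says this interim SAP becomes the study SAP if futility criteria are met, so the definition could be the final one. And this is an open-label trial without a randomized control, so no comparison arm would reveal an undercount.

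**Working it through.** The plan states no figure to reproduce, because the point concerns a definition. The check follows one test case through the AE sections.

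**Test case.** An AE opens between consent and first dose at Grade 1. It reaches Grade 3, or becomes serious, on daratumumab. It is judged not related and stays on one record with its original onset date.

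**Step 1: route one.** The onset date is before the start of study treatment. The second route waives the start date explicitly, which implies that the first route is keyed to it. Route one is not met.

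**Step 2: route two.** The event is judged below possibly related. Route two is not met, so the event is not a TEAE.

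**Step 3: where the event can still appear.**

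| SAP section | Basis | Test case shown? |
|---|---|---|
| 5.1.1 Overview | TEAEs | No |
| 5.1.2 All TEAEs, table and listing | TEAEs | No |
| 5.1.3 Grade 3 or 4 | TEAEs | No |
| 5.1.6 SAEs | Treatment-emergent | No |
| 5.1.8 Delays or modifications | TEAEs | No |
| 5.1.7 Discontinuation | Headed TEAEs; second sentence says AEs, tied to the end-of-treatment CRF page | Possibly |
| 5.1.9 Outcome death | Worded as AEs | Possibly, if fatal |
| 5.2 Deaths | All deaths | Yes, if fatal |
| 3.2 Disposition | Reason for stopping treatment, no TEAE filter | Yes, as a reason, if treatment stops |
| 3.3 Exposure | Delays and modifications by reason (AE or other), no TEAE filter | Yes, as a reason, if dosing is delayed or skipped |
| 5.3 Laboratory | Worst on-treatment grade | Hematology and chemistry only |

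Sections 5.1.4 and 5.1.5 are not affected. An infusion-related reaction cannot begin before the first infusion, and an event judged related already qualifies through route two.

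**Step 4: the alternative recording rule.** If the worsening is entered as a new AE with its own onset date, that record starts after first dose. Route one is met, and the event is counted in every table above that applies to it.

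**Step 5: largest effect per subject.** The Stage 1 cohort sizes in SAP 1.1 are 20 (MCL), 15 (DLBCL) and 15 (FL).

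- MCL: 1/20 = 5.0 percentage points.
- DLBCL or FL: 1/15 = 6.7 percentage points.

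These are ceilings. SAP 5.1 counts a subject once at each level of summary, so a subject who already has another Grade 3 or 4 TEAE changes the overall Grade 3 or 4 incidence by 0. The preferred-term row could still change.

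**The case against.** The strongest objection is that the loss depends on a recording rule outside the supplied text. That rule would sit in the protocol's AE definitions or in the eCRF completion guidelines, which Protocol 17.6 says will be provided. If each worsening gets a new record, no count changes. SAP 5.4 says post-baseline physical examination findings were collected as AEs, which hints at new records but does not settle the matter. This objection stands, and it makes the point conditional. It does not remove it, because the SAP's own definition leaves the result to that rule without stating it.

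A reader might infer more than the documents support, in four ways.

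- *Every AE summary loses such events.* Sections 5.1.7 and 5.1.9 contain wording about AEs rather than TEAEs, although the general TEAE sentence in 5.1 may still govern them. Disposition, exposure, deaths and laboratory worst grades are not TEAE-filtered. For the same reason, a hidden downward bias in discontinuations is not established.
- *Any pre-existing condition is exposed.* SAP 3.1 summarizes medical history separately. A condition held there has no pre-dose AE record, so if it worsens and is reported as an AE, that record would probably begin after dosing and qualify. The exposed group is AEs opened between consent and first dose, about 28 days at most.
- *Each affected subject moves a rate by 5.0 or 6.7 points.* Those are maxima, for the reason in step 5.
- *Such cases are common because symptoms are attributed to lymphoma.* The documents give no rate of pre-dose AEs and nothing on how investigators attribute them. The causality threshold is also low, since possibly related is enough.

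Two further limits are fair. Protocol 12.3.2 requires SAEs to reach the sponsor within 24 hours, so a serious worsening is not lost to oversight, only potentially to a table. The futility guideline in SAP 1.1 counts responses only, so no stopping threshold depends on these tables.

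Finally, the verb in the first route could be read to cover any event still continuing after first dose. That reading would also count baseline events that never change, so the definition would still need clarifying.

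**Conclusion.** The concern holds in conditional form. SAP 5.1 has no worsening clause. An AE is left out of sections 5.1.1 to 5.1.3, 5.1.6 and 5.1.8, where they would otherwise apply, if four conditions all hold: it opened between consent and first dose; it rose in grade or became serious on treatment; it was judged not related; and it stayed on its original record. Under those conditions the rule can only remove events, so any bias in those rates is downward.

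The total size cannot be estimated from the documents. Per affected subject, the effect on a Stage 1 incidence lies between 0 and 5.0 points (MCL) or 0 and 6.7 points (DLBCL, FL), and it is 0 if worsening is always entered as a new AE. The conclusion assumes that the first route is applied by onset date, as the wording of the second route implies. The tables are descriptive and test no hypothesis, but they form the safety account of the trial, so the definition is worth correcting.

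**What to change.** In SAP 5.1, add a third route to the definition: *or any AE present before the first dose that increases in toxicity grade or becomes serious after the first dose and within the window*. Add a derivation rule that takes the date and grade of worsening as the TEAE onset and grade. If the eCRF already opens a new record at each worsening, state that in SAP 5.1 as well; the clause then changes no count.

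The cost is one clause and one derivation rule. TEAE counts may rise slightly. Where grade changes sit on a single record, the date of worsening has to be available or entered.
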